### (b) Inclusion criteria

- i) Female and male adolescents of Hispanic immigrant origin, defined by at least one parent born in a Spanish speaking country of the Americas. Parent must understand Spanish given that parent sessions are delivered in this language. In past studies, over 99% of all Hispanic parents understood Spanish.
- ii) Adolescent between the ages of 12 – 16 years
- iii) Adolescent living with an adult primary caregiver who is willing to participate
- iv) Families must have broadband Internet access on a device, including (but not limited to) a smartphone, iPad, tablet, computer at their home or other location (e.g., school, library, etc.)

(c) Exclusion Criteria

- i) Families reporting plans to move out of the South Florida area during the study.
- ii) Families reporting that adolescent has been diagnosed with a developmental delay.

(d) Screening for Eligibility

Clinic staff will let the research team know between a day and two weeks before whether they have Hispanic youth ages 12 - 16 scheduled to come into the clinic and if so at what time. When the potentially eligible family checks in, the family will be moved to a small office space where the assessor and/or facilitator will be. The assessor and/or facilitator will screen parent and youth (separately) by asking parents pre-defined screening questions (i.e. the inclusion criteria). If the participant declines at any moment, verbal consent or assent will be asked for the participant to complete a brief questionnaire.

Additionally, we will do the following:

a) UM/Jackson patients (parents only) will receive a letter (hand delivered, e-mail and/or mail) from their physicians informing them about the study. This letter will inform participants that they will be receiving a call from research study personnel to see if they are interested in participating. Additionally, a phone number will be provided for the potential parent participant to contact research personnel.

b) Research study staff will request permission from each clinic to have access to their scheduling system. On a daily basis, research study personnel will access data on which individuals have a scheduled appointment. No health information will be available to research study staff, only whether there is an appointment scheduled. Study staff will screen these individuals, at the clinic, to see which meet criteria. Study staff will then go to waiting room to recruit those that meet criteria.

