Family functioning (reported by both youth and parents) consists of parental investment in the adolescent and parent-adolescent communication. Parental investment in the adolescent will be assessed using 1) the Parenting Practices (Loeber et al., 1999), and 2) the Family Relations Scale (Tolan et al., 1997). Two subscales of the Parenting Practices: (a) extent of parental involvement (20 items) and (b) positive parenting (9 items) will be used to assess parental investment. Cronbach's alpha for the two (parent reported) subscales were .83 and .78, respectively. Cronbach's alpha for the two (adolescent reported) subscales were .86 and .85, respectively. The Family Relations Scale assesses the amount of social support the adolescent receives from the parent (6 items) (Tolan et al., 1997). Cronbach's alpha for this subscale is .73 (parents) and .70 (youth).

Communication will be assessed via the Parent-Adolescent Communication Scale (Barnes & Olson, 1985), which assesses the quality and content of communication between parents and youth. Youth report on the quality and content of communication they perceive with their parent. In the parent version, parents report on their perception of the quality and content of their communication with their youth. Cronbach's alpha coefficients for this measure was .85 (parents) and .93 (youth).

Youth's own sexual risk behaviors will be assessed using a 22-item instrument from Jemmott, Jemmott, and Fong (1998). This self-report measure will be used to document the number of times youth report having sex (oral, vaginal, and anal) in their lifetime and in the past 3 months. This instrument is also used to document the number of times youth has been exposed to situations of high risk during sexual intercourse (e.g. having unprotected sex and/or being under the influence of alcohol or drugs while having sex). This measure also asks participants whether they have sex with males and/or females.

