## 12) Data Management\*

### (a) Data Analysis Plan and Power Analysis

**H1a:** *eHealth Familias Unidas Primary Care will be effective, relative to Care as Usual, in reducing the frequency of (past 90-day) drug use in Hispanic adolescents over time.*

This hypothesis will be analyzed using Latent Growth Modeling (LGM). Growth models can be expressed in terms that are identical to models using random coefficients regression, mixed models or multi-level models, where the first level fits each response in time to an individual-level growth model. The second level represents the condition effect on the slope of drug use. LGM analyses will test for differences in trajectories of drug use over the 5 assessment time points among the 2 conditions. As recommended by Raudenbush and Bryk, we will use 2-level analysis to determine whether the mean trajectories of drug use for eHealth Familias Unidas Primary Care and prevention as usual differ significantly over time. Data analysis for this hypothesis and all others will be conducted using Mplus (v 7.2).

Power. Mplus Monte Carlo simulation with 10000 replications was used to calculate the power for this hypothesis using a latent growth curve model framework with one covariate (i.e., condition assignment) and missing data. With 5 time points (0, 6, 12, 24 and 36 months) and assuming a 5% attrition rate at each assessment (also assuming equal sample size across both conditions), with 228 cases in each condition at baseline (or 185 at the final assessment timepoint in each condition), we have 80% power to detect a regression coefficient equal to 0.09 (effect size = 0.3) in the regression of the slope growth factor on intervention condition. This is considered slightly over a small (0.2) effect size.

**H1b:** *eHealth Familias Unidas Primary Care will be effective, relative to prevention as usual, in reducing the frequency of (past 90-day) unprotected sex in Hispanic adolescents over time.*

The analytic plan and power analysis for this hypothesis are similar to that of H1a.

**H1c:** *eHealth Familias Unidas Primary Care will be effective, relative to prevention as usual, in reducing STI incidence (specifically, the incidence of gonorrhea and chlamydia).*

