This hypothesis will be analyzed using a univariate logistic regression for the binary outcome, new diagnoses of STIs (Yes/No). STI incidence will be defined as a positive laboratory test result for a new chlamydia or gonorrhea infection at any of the four follow up assessment timepoints. In the analysis for this hypothesis, condition will predict STI diagnosis. The test of the hypothesis will be based on a Wald test comparing the intervention regression coefficient to its standard error. Additionally, the time of STI diagnosis will be included as a covariate in the logistic regression to test the robustness of the intervention's effect.

**Power.** According to CDC national statistics, the annual STI incidence rate is 3.16% for Hispanic adolescents aged 15 to 19. Thus, we expect the 3-year STI incidence rate in the control group to be approximately 9.2%. Using a one-sided Z test with pooled variance to test the difference between two independent proportions (assuming the same 5% attrition rate at each assessment timepoint), the study has over 80% power to detect a difference of 6.1% in STI incidence between the two conditions. This difference in proportions translates to an effect size of Cohen's  $h = 0.26$ , considered a small ( $h = 0.2$ ) to medium ( $h = 0.5$ ) effect size, according to Cohen (1988).

**H2a:** *Intervention effects on frequency of drug use will be partially mediated by improvements in family functioning over time.*

To test for mediation, we will use the "product of coefficients" test described by MacKinnon and colleagues, which is based on the distribution of the indirect effect of the intervention through the mediator (Cohen, 1988). This procedure tests whether the product of the coefficients from the intervention to the mediator (a) and from the mediator to the outcome (b) is significantly different from zero. Specifically, we will estimate paths between intervention and family functioning (a), and between family functioning and drug use (b). Because we have five time points, our first mediation analyses will fit bivariate growth curves for both family functioning and drug use and examine the role of the (latent) slope of family functioning on the slope of

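### The H1c robustness model adjusts for time of STI diagnosis, which undiagnosed youths do not have; prespecified baseline covariates should replace it and would cheaply help H1a and H1b

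*Combined protocol and SAP*

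**What the plan says.** All three primary analyses are in section 12(a).

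- **H1c, main model:** "This hypothesis will be analyzed using a univariate logistic regression for the binary outcome, new diagnoses of STIs (Yes/No". Condition is the predictor, and the test is a Wald test. The outcome is one yes/no value per youth across the four follow-up assessments.
- **H1c, robustness model:** "the time of STI diagnosis will be included as a covariate in the logistic regression".
- **H1a:** "The second level represents the condition effect on the slope of drug use". Its power simulation used a "latent growth curve model framework with one covariate (i.e., condition assignment) and missing data". H1b is described as similar. The baseline assessment is the first of the five time points in both.
- **Software:** "Data analysis for this hypothesis and all others will be conducted using Mplus (v 7.2".

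Two natural baseline covariates are already collected under section 10(c). Age is on the demographics form, and the sexual-risk instrument is used to "document the number of times youth report having sex (oral, vaginal, and anal) in their lifetime and in the past 3 months". Section 5(b) sets the entry age: "Adolescent between the ages of 12 – 16 years".

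**The concern.** There are two parts, of unequal weight.

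First, the only covariate that the plan adds to H1c is a consequence of the outcome. A youth has a time of diagnosis only if diagnosed, so the covariate largely encodes the outcome. A model containing it cannot show whether the intervention effect is robust.

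Second, no primary analysis uses a baseline covariate beyond the baseline outcome in the growth models. Entrants aged 12 to 16 are followed for 36 months, so at the last visit they are about 15 to 19 and may differ widely in exposure to STI risk. If age and sexual experience are prognostic, leaving them out gives up some precision. If they are added only after the data have been seen, the adjustment may look chosen for its result.

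**Working it through.** **1. Time of STI diagnosis as a covariate.** Follow-up visits are at 6, 12, 24 and 36 months, with one record per youth. The plan does not say what value an undiagnosed youth receives. Three simple choices:
- *Left missing and dropped:* only cases remain, and the outcome does not vary.
- *Coded 0:* every positive time is a case and every zero is a non-case, so separation is complete.
- *Coded 36 months:* every record at 6, 12 or 24 is a case, and only the records at 36 are mixed. The likelihood keeps rising as the time coefficient goes to minus infinity. In the limit, the earlier cases no longer inform the condition effect.

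A simulation of the third coding (185 per arm, 9.2% v 3.1%, diagnosis times spread evenly over the four visits) gave a finite estimate in 0 of 1,000 fits.

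**2. The plan's own H1c power.** Inputs from section 12(a): annual rate 3.16%, 228 per arm, 5% attrition per assessment, control 9.2%, difference 6.1 points, one-sided pooled Z test. Alpha is not stated; 0.05 is assumed.
- Three-year rate: 1 - (1 - 0.0316)^3 = 9.18%.
- Retained: 228 × 0.95^4 = 185.7; 185 is used.
- Mean risk (0.092 + 0.031)/2 = 0.0615. Null SE = sqrt(2 × 0.0615 × 0.9385/185) = 0.0250. Alternative SE = sqrt(0.092 × 0.908/185 + 0.031 × 0.969/185) = 0.0248.
- One-sided power = Phi((0.061 - 1.645 × 0.0250)/0.0248) = 78.9%, close to the stated figure of over 80%.
- Two-sided at 0.05, the same inputs give 68.7%.

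**3. Events available.** 185 × 0.092 + 185 × 0.031 = 17.0 + 5.7 = 22.8, or about 7.6 per coefficient with condition and two covariates.

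**4. H1c power with age and lifetime sexual activity.** The documents give neither prognostic strength nor prevalence, so both are assumed. There were 20,000 replicates per scenario, with ages 12 to 16 in equal shares, half female, sexual activity rising with age, marginal risks held at 9.2% and 3.1%, and a Firth fit where a covariate separates. One-sided 0.05, 12% ever sexually active:

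| Log-odds: per year of age / female / ever active | Unadjusted | Adjusted |
|---|---|---|
| 0 / 0 / 0 | 80.2% | 79.7% |
| 0.2 / 0.3 / 0.7 | 79.7% | 80.0% |
| 0.4 / 0.5 / 1.0 | 80.0% | 81.0% |
| 0.6 / 0.7 / 1.5 | 79.9% | 82.9% |
| 0.6 / 0.7 / 2.5 | 80.3% | 86.8% |

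At 25% ever active, the changes in the same order are -0.1, +0.3, +0.9, +3.2 and +5.1 points. One-sided type I error is 4.6% to 5.2%. A covariate separated in at most 6.5% of adjusted fits.

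A second simulation (3,000 replicates, 20% ever active, odds ratios 1.5 to 15 for ever active and 1.2 to 1.5 per year of age) agrees: one-sided power is 79.6% to 80.9% unadjusted and 79.6% to 85.2% adjusted. Two-sided, it is 66.9% to 68.2% unadjusted and 68.8% to 76.3% adjusted.

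**5. H1a.** The growth-model variances are not given, so the plan's 80% cannot be rerun. Suppose slope variance is a share s of the variance of the estimated effect, and age explains R² of the slope variance. Two-sided power at 0.05 is then Phi(2.80/sqrt(1 - s × R²) - 1.96):
- s = 0.3: 81.2% (R² = 0.10), 82.4% (R² = 0.20).
- s = 0.5: 82.0% (R² = 0.10), 84.0% (R² = 0.20).
- Uninformative covariate: about 79.9%.

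**The case against.** The main H1c test has no defect. Randomisation makes the condition-only comparison valid, and prespecifying a univariate model is legitimate. The gain from adjustment rests wholly on assumed prognostic strengths. The plan's figure, "the annual STI incidence rate is 3.16% for Hispanic adolescents aged 15 to 19", is one rate for one age band and does not show an age gradient within this cohort. Adjustment also puts two more terms on about 23 events, makes the odds ratio conditional and may need software beyond Mplus. All of this stands, and it is why the second part is only an improvement.

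On the first part, the authors may have meant a discrete-time survival analysis, or may code non-cases at their last attended visit. The second coding could avoid exact separation through dropouts, so it would be too strong to say that no coding can be fitted. But the text describes one binary outcome per youth and gives no coding, and any such covariate is still determined after randomisation.

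A reader might infer more than the documents support:
- *The unadjusted test is biased by chance imbalance.* It is not, because its standard error already allows for imbalance. At an assumed 15% prevalence, a gap of 5 points or more in sexual experience has probability 13.5% with 228 per arm (17.8% with 185). It would move an arm's STI risk by about 0.3 to 0.9 points, or up to 1.7 with a very strong effect, against a standard error of about 2.5 points.
- *Adjustment rescues H1c power.* Two-sided, no scenario reached 80%.
- *Randomisation was unstratified, or sex is not recorded.* Parts of the protocol were removed before review, and the section 10(c) list is a summary. Neither inference is safe.

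**Conclusion.** The time-of-diagnosis covariate is wrong as written and should go. It is a post-randomisation value that undiagnosed youths lack, and under the obvious codings the model has no usable fit. The fault is confined to the robustness model and does not touch the condition-only test.

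The absence of baseline covariates is a cheap, low-priority improvement. For H1c, power changes by about -0.5 to +3 points at an assumed one-sided 0.05 with 185 per arm, and by about +5 to +6.5 only if sexual experience is very strongly prognostic. At two-sided 0.05 the base is about 67% to 68%, and adjustment does not restore 80%; the plan states neither alpha nor the sidedness of the Wald test. For H1a the gain is about 1 to 4 points at two-sided 0.05 under the assumed variance shares. No figure is offered for H1b, because the documents give no variance for it. If the covariates carry no information, the loss is under 1 power point.

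**What to change.** Amend section 12(a) before outcome data are seen.

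**H1c.** Delete time of STI diagnosis. Prespecify a logistic model with condition, baseline age and lifetime sexual activity (ever/never) as the model that carries the test, and report the unadjusted result alongside. Add no clinic terms, given about 23 expected events. Name a Firth penalised fit, and the software for it, as the fallback if a covariate separates. State that the odds ratio is conditional, or report a standardised risk difference. For scale, 9.2% v 3.1% is an odds ratio of 0.32 unadjusted and about 0.28 conditional in the fourth scenario tabulated.

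**H1a and H1b.** Add baseline age as a predictor of the growth intercept and slope. Leave the condition paths exactly as planned: this change adds no path from condition to the intercept, which could cost more power than age recovers. Add no clinic-type term. If the H1b model does not converge, use the condition-only model. This is a real possibility: in the school effectiveness study described in section 4(b), 130 of 746 youths (17.4%) were sexually active, and at that rate (an assumption here) 456 families would give about 79.

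**Cost.** SAP wording and no new data collection. H1c gains two terms, each growth model gains two paths, the H1c odds ratio becomes conditional, and a second software package may be needed for the fallback.

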- Frequency of (past 90-day) unprotected sex in Hispanic adolescents over time.
- STI incidence (specifically, the incidence of gonorrhea and chlamydia).

ii) Secondary:

- Improvements in family functioning over time (e.g. parent-adolescent communication, parental monitoring of peers).
- Frequency of unprotected sex will be partially mediated by improvements in family functioning over time.
- Reduction of STI incidence will be partially mediated by improvements in family functioning and decreases in unprotected sex over time.

(b) Safety endpoints

Not applicable.

10) **Procedures Involved**

(a) Study Design

This study tests the effectiveness of eHealth Familias Unidas Primary Care in preventing drug use, unprotected sexual behavior, and STIs in a universal sample of Hispanic youth, this study will use a randomized trial design with two levels of intervention (eHealth Familias Unidas Primary Care and prevention as usual) as the between subjects factor with five repeated measures assessments at baseline, 6, 12, 24, and 36 months post baseline as the within subject factor.

Once both primary care giver and adolescent have completed the consent/assent, they will complete the baseline assessment electronically. Once the baseline assessment is complete, they will be randomized to one of the two conditions: eHealth Familias Unidas Primary Care (experimental prevention as usual (control) Condition. Please see attached for consent/assent forms (in English and Spanish). All consent forms will be completed electronically. All confidential study participant information will be stored electronically in secure University of Miami systems.

i) eHealth Familias Unidas Primary Care

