In addition to the self-report measures described above, we will measure gonorrhea and chlamydia by a real-time PCR assay for the direct, qualitative detection of the plasmid DNA of *Chlamydia trachomatis* and the genomic DNA of *Neisseria gonorrhoea* which is currently being used in clinical practice and clinical trials at our institution. This assay has shown high sensitivity and specificity for the detection of both organisms in asymptomatic and symptomatic patients. Youth who test positive for an STI will be referred to treatment. Youth will also be encouraged to refer sex partners for treatment. The county health department will be notified of reportable STIs. For analyses, sexually transmitted infection incidence will be defined as a positive laboratory test result for a new chlamydia or gonorrhea infection at any of the five assessment time points. Previous studies with ethnic minority youth have demonstrated feasibility and a high acceptance rate with respect to the collection of biological markers for determining STI incidence.

We would also like to collect data from clinic facilitators, clinic leaders, and physicians to assess organizational level factors and attitudes towards evidence-based interventions. To do this, we will use the below measures:

*Attitudes Towards Evidence-Based Practice Scale (EBP; facilitator; 15 items): this measure will be administered to facilitators to assess their views on evidence-based practices.*

*Multifactor Leadership Questionnaire (clinic leaders/physician, 21 items): this measure will be administered to clinic leaders/physicians to assess transformational and transactional leadership behavior.*

*Implementation Leadership Scale (ILS; Clinic leaders/physicians, 11 items): this measure assesses the degree to which organizational leaders support their staff in the implementation of evidence-based interventions*

*Implementation Climate Scale (clinic leaders/physician, 18 items): assesses the level of a strategic organizational climate within an organization.*

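### H1c reduces four STI tests to one Yes/No outcome with no analysis set and no allowance for length of follow-up, so the reported incidence, and the comparison if dropout differs by arm, depend on an unstated coding

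*Combined protocol and SAP*

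**What the plan says.** Section 12(a), H1c, sets the model: "This hypothesis will be analyzed using a univariate logistic regression for the binary outcome, new diagnoses of STIs (Yes/No". The outcome is "a positive laboratory test result for a new chlamydia or gonorrhea infection at any of the four follow up assessment timepoints", and condition is the predictor, tested by a Wald statistic. As a robustness check, "the time of STI diagnosis will be included as a covariate in the logistic regression".

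Section 10(a) schedules "five repeated measures assessments at baseline, 6, 12, 24, and 36 months post baseline". Attrition enters only through the power text: H1a is powered "assuming a 5% attrition rate at each assessment", with 228 per arm at baseline and 185 at the end, and H1c "assuming the same 5% attrition rate at each assessment timepoint". The H1c power paragraph gives a 3-year control incidence of 9.2%, a detectable difference of 6.1 points, a one-sided pooled Z test and power over 80%. It states neither a sample size nor an alpha.

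Nothing under H1c says who is analyzed or how an adolescent who misses tests or leaves early is coded. The missing data mentioned under H1a belong to the growth-model power simulation.

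**The concern.** One positive test settles a Yes at any visit. A three-year No is known only after the 36-month test. A single binary outcome therefore needs a rule for adolescents followed for part of the period, and the plan gives none. The diagnosis-time covariate does not supply one, because that time does not exist for adolescents who are never diagnosed.

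Two things are at stake on one of three primary endpoints. First, the reported proportion may not be the 3-year incidence on which the study is powered. Second, if retention differs by arm, some codings turn the difference in follow-up into an apparent effect or hide a real one. Only about 24 infections are expected at the design effect, so a few cases matter.

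**Working it through.** **Inputs.** From Section 12(a): 3.16% a year, 9.2% control 3-year incidence, 6.1-point difference (so 3.1% in the intervention arm), 228 per arm and 5% attrition per assessment. Tests are at 6, 12, 24 and 36 months. Assumed: constant hazard, dropout unrelated to STI risk and without return, every infection found at the next attended test, and alpha 0.05 one-sided.

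**The plan's own figures.**
- 3-year incidence: 1 − (1 − 0.0316)³ = 9.18% (stated 9.2%).
- Retention: 228 × 0.95⁴ = 185.7 (stated 185). The share without the 36-month test is 1 − 0.95⁴ = 18.5%, made up of 5.0% never tested after baseline and 4.8%, 4.5% and 4.3% last tested at 6, 12 and 24 months.
- Cohen's h = 0.262 (stated 0.26).
- Power, pooled Z, one-sided 0.05: 78.9% at 185 per arm and 84.3% at 217 per arm (those with at least one follow-up test). Reaching 80% takes 191 per arm.

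**Equal 5% attrition, control arm.** The chance of infection in each interval is 0.9684^s − 0.9684^t, where s and t are its start and end in years: 0.0159, 0.0157, 0.0306 and 0.0296. The chances of attending the test that closes each interval are 0.95, 0.9025, 0.8574 and 0.8145. The sum of products gives the observed positives: 0.0151 + 0.0141 + 0.0262 + 0.0241 = 0.0796.

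| Coding | Control | Intervention |
|---|---|---|
| Leavers as No | 8.0% | 2.7% |
| At least one follow-up test | 0.0796/0.95 = 8.4% | 2.8% |
| 36-month completers only | 9.2% | 3.1% |
| Any positive, complete negatives only | 0.0796/(0.0796 + 0.9082 × 0.8145) = 9.7% | 3.3% |

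The odds ratio is 0.318 (tested at least once) or 0.319 (leavers as No), against a true 0.316. Expected infections with leavers as No: 228 × (0.0796 + 0.0269) ≈ 24.

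**Attrition that differs by arm, no true effect.** The documents give no arm-specific rates; 8% v 4% and 10% v 5% per visit are assumptions, here with the higher rate in the intervention arm. The same formulas give the risk ratios; rejection rates are simulated.

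| Coding | Risk ratio, 8% v 4% | Risk ratio, 10% v 5% | One-sided 5% rejection |
|---|---|---|---|
| Leavers as No | 0.0730/0.0820 = 0.89 | 0.0688/0.0796 = 0.86 | about 10% / 11% |
| At least one test | 0.0793/0.0854 = 0.93 | 0.0764/0.0838 = 0.91 | about 8% |
| Complete negatives only | 0.1009/0.0961 = 1.05 | 0.1035/0.0972 = 1.06 | about 3–3.5% |
| Completers only | 1.00 | 1.00 | 4.5–4.9% |
| Person-time rate comparison | about 1.00 | about 1.00 | about 4–5% |

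Tested two-sided at 5%, leavers-as-No rejects 5.9% / 6.7% and at-least-one-test about 5.3%.

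**True effect, higher attrition in the control arm.** One-sided power falls from about 82% to 73% / 70% with leavers as No, and across the first two codings to 70–76%. The person-time comparison keeps about 81%. At equal attrition, completers-only has about 2–3 points less power than person-time.

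**The case against.** The best defense is that the comparison is sound at the attrition the plan expects: with equal, non-informative dropout the test is valid and the odds ratio hardly changes. That stands.

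A reader might infer that no binary coding can work and that the reported incidence must be wrong. The documents do not support this. Completers-only recovers 9.2% v 3.1% and keeps its error rate under the assumptions used here; weighting or imputing 36-month status would also retain a binary endpoint. But the plan chooses none of these, and completers-only discards positives already observed.

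Nor can 185 per arm be read as the H1c analysis set. That figure is in the H1a power text; the H1c paragraph gives no n, and 185 yields 78.9%, not over 80%.

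A reader might also infer that dropout will differ because only one arm has contact with staff. Section 10(a) withholds services from controls, but the staffing text before Resources Available makes assessors keep in touch between visits to support retention, with no limit to one arm. Section 7(a) pays for visits without regard to arm, and the H1a power text assumes equal arms. Differential dropout is a possibility, not a prediction. The 10–11% false-positive figures are the leavers-as-No extreme, need higher dropout in the intervention arm, and are much milder two-sided. The plan does not fix the sidedness of the Wald test.

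**Conclusion.** The point holds in a conditional form. H1c names no analysis set and does not adjust for follow-up time, although 18.5% are expected to lack the last test. At equal, non-informative attrition the consequence is descriptive: a control proportion between 8.0% and 9.7% depending on an unstated rule. Bias in the comparison requires dropout that differs by arm or is related to STI risk. Over the assumed range, one-sided error runs from about 3% to 11% according to coding, and power can fall to 70–76%.

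These sizes rest on constant hazard, monotone dropout and one-sided 0.05. A person-time comparison stands in for the visit-level model proposed below. This should be settled before unblinded analysis; it is not a defect that invalidates the trial.

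**What to change.** Make the primary H1c analysis a discrete-time model with a complementary log-log link:
- One record per adolescent per follow-up test, up to the first new positive or the last test.
- Terms for interval (6, 6, 12 and 12 months) and condition, with the Wald test on condition and its sidedness and alpha stated.
- When a visit is skipped and a later one attended, let the record span the whole time since the previous test, through an interval-censored likelihood or a log-interval-length offset.
- Report 36-month cumulative incidence by arm, and restate the H1c power for this model with its n and alpha.
- Add a sensitivity analysis for dropout related to STI risk. The model still assumes non-informative dropout, and Section 14 ends research contact on incarceration, one route by which that could fail.

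Also reconcile two passages that decide which tests count. Section 10(c) counts "a new chlamydia or gonorrhea infection at any of the five assessment time points", whereas Section 12(a) counts a new infection "at any of the four follow up assessment timepoints". Section 26 describes follow-up screening as dependent on reported risk behavior, whereas Sections 10(a) and 11 collect a sample at every time point.

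The cost is plan wording and a little more analysis work; no new data are needed if samples are taken at every visit. The result is a hazard ratio with cumulative incidence instead of an odds ratio.

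### H1c is powered on the pooled-variance Z (score) test but decided on a Wald test, which costs about 1 to 3 points of power at planned rates with 185 per arm, more if infections are fewer, and cannot reject when an arm has no events

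*Combined protocol and SAP*

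**What the plan says.** All of this is in section 12(a), Data Analysis Plan and Power Analysis, under H1c, unless noted.

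- Model: "This hypothesis will be analyzed using a univariate logistic regression for the binary outcome, new diagnoses of STIs (Yes/No"), with condition as the predictor. A youth is a case if a new infection is found at any of the four follow-up assessments.
- Decision rule: "The test of the hypothesis will be based on a Wald test comparing the intervention regression coefficient to its standard error".
- Test used for power: "Using a one-sided Z test with pooled variance to test the difference between two independent proportions".
- Rates: "the annual STI incidence rate is 3.16% for Hispanic adolescents aged 15 to 19", from which "we expect the 3-year STI incidence rate in the control group to be approximately 9.2"%.
- Claim: "the study has over 80% power to detect a difference of 6.1% in STI incidence between the two conditions".
- Numbers: under H1a, "with 228 cases in each condition at baseline (or 185 at the final assessment timepoint in each condition"); the H1c calculation works "assuming the same 5% attrition rate at each assessment timepoint".

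No alpha is given for H1c, the Wald test is not said to be one- or two-sided, no expected number of events is given, and no fallback is named for sparse data.

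**The concern.** The plan powers one statistic and decides on another. When events are few, the two differ in a known direction. The Wald statistic divides the log odds ratio by a standard error that is dominated by the reciprocal of the smaller event count, so it is held down just when the intervention arm does well. If that arm has no infections, the coefficient has no finite estimate and the Wald test cannot reject, however many infections occur in the control arm. The score test comes from the same model and has neither problem. STI incidence is one of three primary endpoints and the only one measured in the laboratory. A change of test made after an empty or nearly empty arm had been seen would not be credible, so the choice should be settled in advance.

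**Working it through.** **Inputs.** From section 12(a): control 9.2%; difference 6.1 points, so intervention 9.2 − 6.1 = 3.1%; 185 per arm at the last assessment, 228 at baseline. Assumed: alpha 5%, since none is stated for H1c.

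**The plan's inputs reproduce.** 1 − (1 − 0.0316)³ = 9.18%. 228 × 0.95⁴ = 185.7. Expected cases: 185 × 0.092 = 17.0 and 185 × 0.031 = 5.7, together 22.8.

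**The plan's power reproduces.** With mean rate 0.0615:

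- standard error under the null: √(2 × 0.0615 × 0.9385 / 185) = 0.02498
- standard error under the alternative: √((0.092 × 0.908 + 0.031 × 0.969) / 185) = 0.02478
- one-sided 5% power: Φ[(0.061 − 1.645 × 0.02498) / 0.02478] = Φ(0.80) = 78.9%

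Exact enumeration of the same test gives 81.1%, so the claim of over 80% holds for the test that was powered.

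**The two statistics at the expected counts.**

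- Score: 0.061 / 0.02498 = 2.44.
- Wald: log odds ratio = ln[(0.092/0.908) / (0.031/0.969)] = 1.153. Its standard error is √(1/17.02 + 1/5.735 + 1/167.98 + 1/179.27) = 0.495, so z = 2.33. Of the variance of 0.245, the term for the smaller count supplies 0.174.

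**Exact power.** Every possible pair of event counts was enumerated with binomial probabilities, counting rejection in favour of the intervention (z above 1.96 for two-sided 5%, above 1.645 for one-sided 5%). A zero cell counts as non-significant for Wald. The rates below 9.2% are assumptions at about the same relative reduction.

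| Per arm | Control v intervention | Expected events | Two-sided: Wald / score | One-sided: Wald / score |
|---|---|---|---|---|
| 185 | 9.2% v 3.1% | 22.8 | 67.0 / 70.3% | 79.7 / 81.1% |
| 228 | 9.2% v 3.1% | 28.0 | 78.0 / 79.1% | 87.3 / 87.4% |
| 185 | 5% v 1.7% | 12.4 | 29.8 / 42.6% | 49.1 / 56.7% |
| 185 | 3% v 1% | 7.4 | 7.5 / 25.8% | 21.2 / 44.0% |

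**Type I error, 185 per arm, two-sided 5%.** At a common rate of 9.2%, Wald 4.7% and score 5.0%; at 6.15%, 4.1% and 4.9%; at 3%, 2.1% and 4.7%. At one-sided 5% the score test reaches at most 5.3% over these rates. The likelihood-ratio test is somewhat liberal: 5.7% at 6.15% and 6.5% at 3%.

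**Empty arm.** The chance of no infection in the intervention arm is (1 − 0.031)¹⁸⁵ = 0.3% at planned rates, 4% at 1.7% and 16% at 1%. With 10 infections v 0 the score z is 3.21 (two-sided p about 0.001), and Wald gives no usable result. With 8 v 1, score z is 2.36 and Wald z is 1.99.

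**Does Wald ever win?** At 185 per arm and fewer than 100 events in total, there is no table in which Wald rejects for benefit and the score test does not, at 1.96 or at 1.645.

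**The case against.** The strongest reply is that this is a matter of taste at the planned rates. Wald is a standard, prespecified test and it is valid here: its error rate is below nominal, so it creates no false-positive risk. The only sidedness stated for H1c is one-sided, and there the loss is 1.4 points. Moreover, 185 per arm is the least favourable count. A youth who drops out before month 36 can already have had a positive test, and the plan does not restrict H1c to completers. At 205 per arm the loss is 1.6 points two-sided and 0.2 one-sided; at 228 it is about 1 point and 0.1. All of this stands, and it is why the point is graded as an improvement and not as a defect in validity.

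A reader might infer that 18 points are lost at the planned 23 or so events. The documents do not support that. The 18-point figure needs about 7 events, at a 3% control rate that appears nowhere in the plan. There is some reason to consider lower rates, because the cited annual rate is for ages 15 to 19 while section 5(b) enrols at 12 to 16, but the plan gives no rate for the younger group. Nor would the score test rescue H1c there, since its own two-sided power is only 26%.

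A reader might also charge the fall from 81.1% to 70.3% to the Wald test. That gap comes from one- against two-sided testing and is a separate matter.

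Finally, the larger power of the likelihood-ratio test (72.8% at planned rates, two-sided) is not all real gain, because part of it is inflated error. A profile-likelihood interval beside a score test could exclude 1 when the test does not reject.

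**Conclusion.** The mismatch is real and Wald is the weaker choice, but the cost at planned rates is small: with 185 per arm, 3.3 points two-sided or 1.4 points one-sided, the latter just enough to take the planned test below the stated 80%. With 228 per arm it is about 1 point or less. The loss becomes material only if infections are fewer than planned: two-sided, about 13 points at 5% v 1.7% and 18 at 3% v 1%. An empty arm would leave H1c without a usable test, with a chance of 0.3% at planned rates. These figures rest on alpha of 5%, about the plan's relative reduction, independent youths, and a zero cell counted as non-significant for Wald. They do not show that the power calculation is wrong for the test it names, or that the planned analysis is invalid. This is a free improvement.

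**What to change.** In section 12(a), H1c, replace the Wald sentence with one stating that the hypothesis is tested by the score test for condition from the logistic model with condition as its only predictor, without continuity correction, which is the pooled-variance Z test already used for power. State that the odds ratio will be reported with an interval obtained by inverting the score test, so that test and interval agree and the interval still gives a finite limit on the informative side when an arm has no events. State the alpha and sidedness in the same sentence, since neither is given for the H1c test.

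The cost is one or two sentences before the outcome data are seen. No data, visits, sample size or model change. Size stays near nominal (two-sided 4.7 to 5.0%, one-sided at most 5.3%, over the rates checked).
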